8.0 Efficacy Analyses

8.1 General Considerations

The Primary Analysis will be performed after all ongoing subjects have completed the Week 24 visit and the database has been locked. This will be the only and final analysis for the primary and key secondary efficacy endpoints as well as all other efficacy endpoints. All efficacy analyses will be conducted in the ITT Population. In addition, Per-protocol analysis for primary endpoint will be performed. All tests will be 2-sided at an alpha level of 0.05.

Categorical variables and continuous variables will be analyzed using Cochran-Mantel-Haenszel (CMH) and Mixed-Effect Model Repeat Measurement (MMRM) method, respectively.

"Baseline" refers to the last non-missing observation before the first administration of study drug or randomization if no study drug is given. When analyzing rolling-average-based endpoints, Baseline refers to the last available rolling average before the date of first administration of study drug.

8.1.1 Analysis of Efficacy Endpoints by Variable Type

Analysis of Categorical Variables

For ITT Population, frequencies and percentages will be summarized along with 95% confidence interval (CI) based on normal approximation. For ITT Population, pairwise comparisons of upadacitinib vs. dupilumab will be made using CMH test using stratification factor as baseline vIGA-AD categories (vIGA-AD 3 or 4). Point estimates, *p*-value, and 95% CIs for the difference in proportions between upadacitinib and dupilumab will be provided. Construction of CIs for the common risk difference will be based on the Mantel-Haenszel estimate adjusting for stratification factors. Breslow-Day test will be performed to test the homogeneity between strata.

NRI-C will be the primary approach for categorical endpoints (Section 8.2). In addition, the primary endpoint and all key secondary categorical endpoints will be analyzed using MI defined in Section 8.2 as the sensitivity approach. All categorical endpoints will be analyzed using NRI-NC defined in Section 8.2 as the sensitivity approach.

Analysis of Continuous Variables

For ITT Population, the Baseline and visit means will be presented for each treatment group who have both Baseline and post-baseline visit values. For ITT Population, Percent change from Baseline in the treatment groups will be compared using MMRM model as described in Table 1. Point estimates, SE, and 95% CIs of LS mean change from Baseline within treatment groups, and these statistics along with *p*-value between upadacitinib group and dupilumab will be provided.

Table 1. Model of Continuous Variables

Population	Model	Adjust for Stratification Factor(s)
ITT	MMRM model includes the categorical fixed effects of treatment, visit and treatment-by-visit interaction, and the continuous fixed covariates of Baseline measurement.	vIGA-AD categories at randomization

All efficacy endpoints will be analyzed overall and within each stratum of the stratification factors: baseline vIGA-AD categories and age group Analysis model within each stratum will not be adjusted for stratification factors.

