2.2 Study Design Overview

This is a Phase 3b, randomized, double-blind, double-dummy, active comparator-controlled multicenter study that will evaluate the safety and efficacy of upadacitinib versus dupilumab in adults (≥ 18 to ≤ 75 years of age) with moderate to severe AD who

[figure not shown]
are candidates for systemic therapy. Eligible subjects must have a documented history of inadequate response to treatment with topical AD treatments or documented use of systemic treatment for AD within 6 months prior to the Baseline Visit or for whom topical treatments are otherwise medically inadvisable.

The study is comprised of a 35-day Screening Period, a 24-week double-blind treatment period, and an End-of-Treatment Follow-up Visit. The End-of-Treatment Follow-up Visit will be 12 weeks after the last injection. Subjects who meet eligibility criteria will be randomized in a 1:1 ratio to one of the two arms as shown below:

- Treatment A (N = 325): Daily oral doses of upadacitinib 30 mg from the Baseline visit until the Week 24 visit, and placebo pre-filled syringe administered at the baseline visit (2 subcutaneous [SC] injections), followed by placebo pre-filled syringe (1 injection) every other week until the Week 22 visit.
- Treatment B (N = 325): Dupilumab 600 mg (2 × 300 mg dupilumab SC injection) administered at the Baseline visit, followed by dupilumab 300 mg SC injection every other week until the Week 22 visit and daily oral doses of placebo tablets from the Baseline visit until the Week 24 visit.

Randomization will be stratified by baseline disease severity (moderate validated Investigator Global Assessment for atopic dermatitis [vIGA-AD 3] vs. severe [vIGA-AD 4]) and age (< 40, ≥ 40 to < 65, ≥ 65 years). The subject's age at baseline will be used for randomization and throughout the duration of the study.

The schematic of the study is shown in [Figure 1](#).

Figure 1. **Study Schematic**

BL = Baseline; SC = subcutaneous

* Dupilumab 300 mg SC injection will be administered every other week starting at the Week 2 visit and until the Week 22 visit, after an initial dose of 600 mg at the Baseline visit.

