3.2 Secondary Endpoints

Ranked Secondary Endpoints:

- Percent change in Worst Pruritus numerical rating scale (NRS) from Baseline at Week 16
- Proportion of subjects achieving a 100% reduction in EASI (EASI 100) at Week 16
- Proportion of subjects achieving a 90% reduction in EASI (EASI 90) at Week 16
- Percent change in Worst Pruritus NRS from Baseline to Week 4
- Proportion of subjects achieving a 75% reduction in EASI (EASI 75) from Baseline at Week 2
- Percent change in Worst Pruritus NRS from Baseline to Week 1

- Proportion of subjects achieving an improvement (reduction) in Worst Pruritus NRS ≥ 4 from Baseline at Week 16.

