3.3 Other Efficacy Endpoints

All variables listed as primary or secondary endpoints will be analyzed at all visits other than Week 16. In addition, the following variables will be analyzed at all visits:

- Proportion of subjects achieving 75% reduction in EASI in the head and neck body region from Baseline
- Proportion of subjects achieving 75% reduction in EASI in each body region (other than head and neck) from Baseline

Proportion of Subjects Achieving an Improvement (Reduction) in Daily Worst Pruritus NRS ≥ 4 from Baseline for Subjects with Daily Worst Pruritus NRS ≥ 4 at Baseline by Day Up to Day 28

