8.6 Efficacy Subgroup Analyses

To evaluate the consistency of the efficacy over demographic and other Baseline characteristics, the primary endpoint will be analyzed in the following subgroups.

- Age Group (< 40 years, \geq 40 – < 65 years, \geq 65 years)
- Sex (male, female)
- BMI (normal: < 25, overweight: \geq 25 – < 30, obese: \geq 30)
- Race (White, Asian, Black, and Other)
- Weight (< median, \geq median)
- Geographic regions (US/PR/Canada, Other)
- Baseline vIGA-AD (moderate or milder [vIGA-AD \leq 3], severe [vIGA-AD 4])
- Baseline EASI (< median, \geq median)
- hsCRP (< median, \geq median)
- Previous systemic therapy (with and without)

Any RACE subgroups with fewer than 10% subjects will be combined with Other for analyses. Age \geq 65 years or BMI \geq 30 subgroups will be combined with their adjacent subgroup when having fewer than 10% subjects. For any subgroup, if there are zero subjects within a stratum in any treatment group, the CMH model will not be adjusted by the stratification factors.

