3.0 Sample SAS Code

```
/*IMPUTATION STEP – DETERMINE IMPUTATION DISTRIBUTION AND RANDOMLY
IMPUTE MISSING VALUE TO GENERATE 'COMPLETE' DATASETS*/
/*****************/
PROC MI DATA=EASI_MONO OUT=EASI_FULL NIMPUTE=1 SEED= 22040 /*RANDOM
SEED PRE-DEFINED*/
    ROUND=. . . 0 1 0 1 0 1 0 1 0 1 0 1 0 1 0 1 0 1 0 1 /*VALUE ROUND TO 1ST
DECIMAL*/
    MIN=. . . 0 0 0 0 0 0 0 0 0 0 0 0 0 0 0 0 0 0 0 0 0 0 /*MINIMUM VALUE OF EASI IS
0*/
    MAX=. . . 72 72 72 72 72 72 72 72 72 72 72 72 72 72 72 72 72 72 72 72 72 72 /*MAXIMUM VALUE OF EASI IS
72*/
    MINMAXITER=1000;
    CLASS TRT01PN VIGAN SEXN;
    VAR TRT01PN VIGAN SEXN BASE WK1 WK2 WK4 WK8 WK12 WK16 WK20 WK24;
    MONOTONE REG (WK1 WK2 WK4 WK8 WK12 WK16 WK20 WK24); /* IMPUTED
SEQUENTIALLY, FROM WK 1 TO 24, WITH COVARIATES CONSTRUCTED FROM THE
CORRESPONDING PRECEDING VARIABLES*/
    BY _IMPUTATION_; /*FOR EACH OF THE 30 MONOTONE
MISSING DATASETS, IMPUTE A 'COMPLETE' DATASET*/
RUN;

/*DETERMINE DICHOTOMOUS RESPONSE STATUS, EASI 75*/
DATA ALL; SET EASI_FULL;
    IF 0<=WK1<=0.25*BASE THEN EASI75_1=1;
    ELSE EASI75_1=0;
    IF 0<=WK2<=0.25*BASE THEN EASI75_2=1;
    ELSE EASI75_2=0;
    IF 0<=WK4<=0.25*BASE THEN EASI75_4=1;
    ELSE EASI75_4=0;
    IF 0<=WK8<=0.25*BASE THEN EASI75_8=1;
    ELSE EASI75_8=0;
    IF 0<=WK12<=0.25*BASE THEN EASI75_12=1;
    ELSE EASI75_12=0;
    IF 0<=WK16<=0.25*BASE THEN EASI75_16=1;
    ELSE EASI75_16=0;
    IF 0<=WK20<=0.25*BASE THEN EASI75_20=1;
    ELSE EASI75_20=0;
    IF 0<=WK24<=0.25*BASE THEN EASI75_24=1;
    ELSE EASI75_24=0;

RUN;

/*****************/
/*
/*          DATA HANDLING STEPS TO MERGE COVID-19 STATUS OMITTED
*/
```

```

/*
   PLACE TO ADD DATA HANDLING AND MERGING STEPS
*/
*****

/*FOR MI, SKIP THE FOLLOWING CODE, PROCEED TO THE CODE AFTER ANALYSIS
MODEL *//*OVERRIDE MISSING VALUES NOT DUE TO COVID-19 WITH TRADITIONAL
NRI*/
DATA ALLF; SET ALL;
  /*COVID19_XX='Y' IF MISSING AT WEEK XX IS DUE TO COVID-19; IF NOT,
OVERRIDE WITH TRADITIONAL NRI*/
  IF COVID19_1 NE 'Y' THEN EASI75_1=EASI75NRI_1;
  IF COVID19_2 NE 'Y' THEN EASI75_2=EASI75NRI_2;
  IF COVID19_4 NE 'Y' THEN EASI75_4=EASI75NRI_4;
  /*VARIABLE EASI75NRI XX: TRADITIONAL NRI DATA AT WEEK XX, WHICH COVERS
THE SPECIAL HANDLING SUCH AS THE BEFORE-AND-AFTER EXCEPTION*/
  IF COVID19_8 NE 'Y' THEN EASI75_8=EASI75NRI_8;
  IF COVID19_12 NE 'Y' THEN EASI75_12=EASI75NRI_12;
  IF COVID19_16 NE 'Y' THEN EASI75_16=EASI75NRI_16;
  IF COVID19_20 NE 'Y' THEN EASI75_20=EASI75NRI_20;

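### Single-arm response-rate intervals use the normal approximation with no rule for sparse cells, so some descriptive 95% intervals would under-cover or shrink to zero width (minor)

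*SAP*

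**What the plan says.** SAP 8.1.1 has one rule for response rates in the ITT Population: "frequencies and percentages will be summarized along with 95% confidence interval (CI) based on normal approximation". It names no exact or score interval and no minimum number of responders. The treatment comparison has its own methods in the same section: a CMH test, and a Mantel-Haenszel interval for the risk difference.

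Three other statements set how far the rule reaches.

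- **Visits.** SAP 3.3: "All variables listed as primary or secondary endpoints will be analyzed at all visits other than Week 16". The secondary list in SAP 3.2 includes EASI 90 and "Proportion of subjects achieving a 100% reduction in EASI (EASI 100) at Week 16". The sample code in SAP Appendix F, section 3.0, shows the EASI visits, starting at Week 1: "VAR TRT01PN VIGAN SEXN BASE WK1 WK2 WK4 WK8 WK12 WK16 WK20 WK24".
- **Strata.** SAP 8.1.1: "All efficacy endpoints will be analyzed overall and within each stratum of the stratification factors: baseline vIGA-AD categories and age group". SAP 2.2 defines the age strata: "age (< 40, ≥ 40 to < 65, ≥ 65 years".
- **Pooling.** SAP 8.6 says of the age 65-and-over and BMI 30-and-over groups that these "subgroups will be combined with their adjacent subgroup when having fewer than 10% subjects". Section 8.6 covers subgroup analyses of the primary endpoint. The rule is not repeated for the within-stratum analyses of 8.1.1.

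**The concern.** The Wald interval estimates its own width from the observed proportion. With no responders the estimated variance is zero, so the interval has no width. With very few, it is too narrow and its lower limit can fall below zero.

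The plan can lead to such cells in two ways. EASI 100 means complete clearance in subjects who enter with EASI of at least 16 (Protocol 5.1), so very low rates at Weeks 1 and 2 are plausible. The age 65-and-over stratum may also be small; the pooling rule in SAP 8.6 allows for that.

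At stake is the honesty of the printed error bars. Where the data are thinnest, an interval labelled 95% would claim more certainty than it has.

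**Working it through.** **Inputs from the documents.** 325 subjects per arm; dupilumab EASI 75 rate of at most 50%; difference of 12 percentage points, hence 62% (SAP 2.4); interval method (SAP 8.1.1).

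**Assumptions, not in the documents.** True early rates of 0.2% to 10%. Age-stratum sizes of 20 per arm (20/325 = 6%) and 33 per arm (33/325 = 10%). The SAP gives no formula for the normal approximation; I read it as Wald.

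**The plan's own figure.** SAP 2.4 claims more than 80% power. The standardised value is (0.12·√325 − 1.96·√(2·0.56·0.44)) / √(0.50·0.50 + 0.62·0.38) = (2.163 − 1.376)/0.697 = 1.13, so power is 87%. The claim holds. The plan states no coverage figure to reproduce.

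**Formulas.** With x responders of n and p̂ = x/n:

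- Wald: p̂ ± 1.96·√(p̂(1 − p̂)/n)
- Wilson: [p̂ + 1.96²/(2n) ± 1.96·√(p̂(1 − p̂)/n + 1.96²/(4n²))] / (1 + 1.96²/n)
- Exact coverage at true rate p: the sum of the binomial probabilities of every x whose interval contains p.

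**Example.** At n = 325 and p = 0.2%, the Wald interval contains p only for x = 1 to 4. The chance of x = 0 is 0.998^325 = 52.2%, and that outcome always misses. Coverage is therefore 47.8%.

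**Full arm, n = 325.**

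| True rate | Chance of 0 responders | Wald coverage | Wilson coverage |
|---|---|---|---|
| 0.2% | 52.2% | 47.8% | 97.2% |
| 0.5% | 19.6% | 80.2% | 97.5% |
| 1% | 3.8% | 83.5% | 95.3% |
| 2% | 0.1% | 88.4% | 95.7% |
| 5% | <0.1% | 92.2% | 94.5% |
| 10% | <0.1% | 94.1% | 95.9% |
| 50% | <0.1% | 95.4% | 95.4% |
| 62% | <0.1% | 95.4% | 94.8% |

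**Small strata (sizes assumed).**

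| n per arm | True rate | Wald coverage | Wilson coverage |
|---|---|---|---|
| 20 | 5% | 63.9% | 92.5% |
| 20 | 10% | 87.6% | 95.7% |
| 33 | 5% | 81.1% | 97.7% |
| 33 | 10% | 85.2% | 95.8% |

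By symmetry, the 10% rows also hold at 90%.

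**Printed intervals.**

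- 0/325: Wald 0 to 0. Wilson upper limit 1.96²/(325 + 1.96²) = 3.84/328.84 = 1.17%.
- 1/325: Wald −0.29% to 0.91%; Wilson 0.05% to 1.72%.
- 0/33: Wald 0 to 0; Wilson 0 to 10.4%.
- 163/325: Wald 44.7% to 55.6%; Wilson 44.8% to 55.6%.

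These calculations treat every response as observed. They do not model the multiple imputation of COVID-19 missing values under NRI-C.

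**The case against.** The strongest reply is that nothing inferential depends on this interval. The primary test, the ranked sequence in SAP 11.0, the risk-difference interval and the sample size all use other methods. At the only response rates the documents supply, 50% and 62%, the Wald interval covers 95.4%. In a full arm, the marked shortfall needs a true rate of about 2% or less, and a reader who sees 0/325 can judge it without an interval. All of this stands, and it limits the point to a minor one.

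It is also fair that the within-stratum sentence in SAP 8.1.1 names no interval method. Applying the normal approximation there is a reading of the section as a whole, though no other single-arm method is offered. The pooling rule in SAP 8.6 would merge an age group of 20 per arm if the other arm were similar, but only for the primary-endpoint subgroups.

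A reader might infer three stronger things, none of which the documents support.

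- **That the early-visit and older-age tables will be wrong.** No early EASI 90 or EASI 100 rate and no stratum size is given, so this is conditional.
- **That low rates in general are badly covered.** In a full arm, coverage is already 92% at 5% and 94% at 10%.
- **That the difference intervals should become score-type as well.** The calculations above show no failure of the planned Mantel-Haenszel interval. Under NRI-C, the Appendix F code passes a risk difference and its standard error to PROC MIANALYZE; score-type intervals do not fit that step directly.

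**Conclusion.** The point holds as a minor correction to descriptive output. The SAP prescribes one interval for all single-arm response rates and provides nothing for cells where it breaks down.

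If early EASI 90 or EASI 100 rates are about 2% or less, full-arm coverage is 88% or lower at the rates checked, reaching 48% at 0.2%. If the age 65-and-over stratum holds about 20 to 33 subjects per arm, coverage is 64% to 81% at a rate of 5% and 85% to 88% at 10%. Any cell without responders prints a zero-width interval, whatever the true rate.

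These sizes rest on the Wald reading, on the assumed rates and stratum sizes, and on fully observed data. The Week 16 EASI 75 intervals in the full arms are sound at the design rates.

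**What to change.** In SAP 8.1.1, replace the normal approximation with the Wilson score interval for single-arm response rates, and say that it applies at all visits and within strata.

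Where NRI-C imputes COVID-19 values, state how the interval is formed over the 30 datasets. One option is to apply Wilson to the pooled proportion p̄ with an effective sample size n* = p̄(1 − p̄)/V, where V is Rubin's total variance of the single-arm proportion. If no dataset has a responder, n* is 0/0, so the text should fall back on the actual number of subjects.

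Leave the CMH test and the difference intervals as they are.

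The cost is a short SAP edit, a software option, and one extra programming step for imputed data. Intervals become slightly wider at extreme rates and barely change at mid-range ones. Wilson is not perfect: it covers 92.5% at n = 20 and a rate of 5%, and 85% at n = 33 and a rate of 0.5%. Wald covers 64% and 15% in those two cases.

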## AD Disease Activity

- ✔ 4. Chronic AD with onset of symptoms at least 3 years prior to baseline and subject meets Hanifin and Rajka criteria.
- ✔ 5. Subject meets all of the following disease activity criteria:
  - EASI score  $\geq 16$  at the Screening and Baseline Visits;
  - vIGA-AD score  $\geq 3$  at the Screening and Baseline Visits;
  - $\geq 10\%$  body surface area (BSA) of AD involvement at the Screening and Baseline Visits;
  - Baseline weekly average of daily Worst Pruritus NRS  $\geq 4$ . Note: The baseline weekly average of daily Worst Pruritus NRS will be calculated from the 7 consecutive days immediately preceding the Baseline Visit. A minimum of 4 daily scores out of the 7 days is needed.
- ✔ 6. Subject has applied a topical emollient (moisturizer) twice daily for at least 7 days before the Baseline Visit. Note: Subject may use prescription moisturizers or moisturizers containing ceramide, urea, filaggrin degradation products or hyaluronic acid if such moisturizers were initiated before the screening visit.
- ✔ 7. Documented history (within 6 months of the Baseline Visit) of inadequate response to TCS or topical calcineurin inhibitors (TCI) OR documented systemic treatment for atopic dermatitis within 6 months prior to the Baseline Visit, OR for whom topical treatments are otherwise medically inadvisable (e.g., because of important side effects or safety risks).

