8.2.1 Categorical Endpoints

- The primary approach for handling missing data in the analysis of categorical endpoints (including the primary endpoint) will use Non-Responder Imputation while incorporating Multiple Imputation (MI) to handle missing data due to COVID-19 (NRI-C).

The NRI-C will categorize any subject who does not have an evaluation during a pre-specified visit window (either due to missing assessment or due to early withdrawal from the study) as a non-responder for the visit. The only exceptions are: 1) when the subject is a responder both before and after the visit window, the subject will be categorized as a responder for the visit. 2) missing data due to COVID-19 infection or logistical restriction will be handled by Multiple Imputation. In addition, all assessments after the start of rescue medications will not be included in the analyses; as a result, subjects will be counted as non-responders thereafter and will not be imputed by MI. NRI-C will not be applied to the endpoint of improvement of daily Worst Pruritus NRS ≥ 4 up to Day 28.

- A sensitivity analysis for categorical endpoints will use NRI with No special data handling for missing due to COVID-19 (NRI-NC).

NRI-NC will be performed in the same way as NRI-C without the exception #2 above. That is, missing due to COVID-19 infection or logistical restriction will also be counted as non-responders.

Subjects whose change/percent change from Baseline cannot be calculated because of a missing Baseline will be considered as a non-responder at all post-baseline visits in both NRI-C and NRI-NC approaches. NRI-NC will be primary approach for the efficacy endpoint of improvement of daily Worst Pruritus NRS ≥ 4 up to Day 28.

- Multiple Imputation (MI), a sensitivity analysis for the primary endpoint and key secondary categorical endpoints: Markov Chain Monte Carlo (MCMC) will be first applied to augment data into monotonic missing pattern and PROC MI will be used to generate 30 datasets using the regression method. The variables to be included in the imputation model are: treatment group, stratum (vIGA-AD categories), gender, Baseline, and measurements at each visit up to the end of the analysis period. The random seed for MCMC and the random

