8.3.3 Primary Efficacy Analysis

For ITT Population, comparisons between each upadacitinib group and the dupilumab group will be conducted using the CMH test, adjusting for vIGA-AD categories. NRI-C will be the primary approach to handle missing values. The NRI-NC and MI approaches will be used as sensitivity analyses.

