8.4 Secondary Efficacy Analyses

8.4.1 Key Secondary Efficacy Analyses

The secondary endpoints for the primary analysis of efficacy are:

- Percent change in Worst Pruritus NRS from baseline to Week 16

- Proportion of subjects achieving at least a 100% reduction in Eczema Area and Severity Index from Baseline (EASI 100) at Week 16;
- Proportion of subjects achieving at least a 90% reduction in Eczema Area and Severity Index from Baseline (EASI 90) at Week 16;
- Percent change in Worst Pruritus NRS from Baseline to Week 4;
- Proportion of subjects achieving a 75% reduction in EASI (EASI 75) from Baseline at Week 2;
- Percent change in Worst Pruritus NRS from Baseline to Week 1
- Proportion of subjects achieving an improvement (reduction) in Worst Pruritus NRS ≥ 4 from Baseline at Week 16

Hypotheses corresponding to the endpoints are:

- The percent change in Worst Pruritus NRS from baseline in subjects treated with upadacitinib for Atopic Dermatitis is greater than that of dupilumab at Week 16.
- The proportion of subjects with EASI 100 treated with upadacitinib for Atopic Dermatitis is greater than that of dupilumab at Week 16.
- The proportion of subjects with EASI 90 treated with upadacitinib for Atopic Dermatitis is greater than that of dupilumab at Week 16.
- The percent change in Worst Pruritus NRS from baseline in subjects treated with upadacitinib for Atopic Dermatitis is greater than that of dupilumab at Week 4.
- The proportion of subjects with EASI 75 treated with upadacitinib for Atopic Dermatitis is greater than that of dupilumab at Week 2.
- The percent change in Worst Pruritus NRS from baseline in subjects treated with upadacitinib for Atopic Dermatitis is greater than that of dupilumab at Week 1.
- The proportion of subjects with an improvement (reduction) in Worst Pruritus NRS ≥ 4 with upadacitinib for Atopic Dermatitis is greater than that of dupilumab at Week 16.

Secondary efficacy endpoints will be analyzed by comparing upadacitinib treatment group and dupilumab. The categorical endpoints and continuous endpoint will be analyzed by CMH and MMRM, respectively, and the corresponding analyses are specified in Section 8.1.

Worst Pruritus NRS will be analyzed based on weekly rolling averages of daily scores.

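### No responder endpoint is adjusted for its own baseline score; for the ranked itch responder endpoint, adding baseline NRS would be a cheap precision gain of roughly 0 to 6 power points

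*SAP*

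**What the plan says.** SAP 8.1.1 sets one method for all categorical endpoints: "pairwise comparisons of upadacitinib vs. dupilumab will be made using CMH test using stratification factor as baseline vIGA-AD categories". The effect estimate follows the same route: "Construction of CIs for the common risk difference will be based on the Mantel-Haenszel estimate adjusting for stratification factors". For the primary endpoint, SAP 8.3.3 says that the comparison "will be conducted using the CMH test, adjusting for vIGA-AD categories". SAP 8.2.1 applies the same single-factor CMH to each multiply imputed dataset, SAP 8.4.1 sends the secondary responder endpoints back to 8.1, and Protocol 7.3 agrees.

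The baseline value of the outcome is used in three other places:

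- The MMRM for continuous endpoints has "the continuous fixed covariates of Baseline measurement".
- The imputation model in SAP 8.2.1 contains "treatment group, stratum (vIGA-AD categories), gender, Baseline, and measurements at each visit"; SAP Appendix F uses the same set.
- SAP 8.6 splits baseline EASI at the median as a subgroup, for the primary endpoint only.

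The itch responder endpoint is "Proportion of subjects achieving an improvement (reduction) in Worst Pruritus NRS ≥ 4 from Baseline at Week 16", seventh and last of the ranked secondary endpoints (Protocol 3.3). Entry requires a "Baseline weekly average of daily Worst Pruritus NRS" of at least 4 (Protocol 5.1, criterion 5), on a scale from 0 to 10 (Protocol 5.10).

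**The concern.** A responder endpoint defined by a fixed absolute drop is harder to reach from a low starting value. Baseline NRS is then likely to predict response. vIGA-AD is a global severity grade assigned by the investigator, not an itch score, and the documents do not show that it carries the same information.

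If baseline predicts response and is left out, two things follow. The variance it explains stays in the standard error of the risk difference, and a chance imbalance in baseline itch between arms is not corrected. What is at stake is precision and power, not validity. The itch responder endpoint is the last test in the fixed sequence of SAP 11.0, so nothing later depends on it; its own precision decides its own claim.

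This point concerns the baseline score of the outcome. It does not concern the age stratum.

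**Working it through.** **1. The plan's own figure.** Inputs from SAP 2.4: 325 per arm, 50% against 62%, two-sided 0.05. With pooled proportion 0.56:

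z = [0.12·√325 − 1.96·√(2·0.56·0.44)] / √(0.50·0.50 + 0.62·0.38) = (2.163 − 1.376)/0.697 = 1.13, so power = Φ(1.13) = 87.1%.

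The stated figure of more than 80% is met. It remains met at 85.3% with a continuity correction.

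**2. The itch criterion.** The relief needed is 4/baseline: 4/4 = 100%, 4/7 = 57%, 4/8 = 50%, 4/10 = 40%. This follows from the definition and the entry floor alone.

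**3. Size for the itch endpoint.** If baseline explains a share R² of the response variance, adjustment acts like 1/(1 − R²) times the sample. A test with 80% power then has power Φ(2.80/√(1 − R²) − 1.96).

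The documents give no baseline NRS distribution, no itch responder rate and no correlation, so everything below is assumed. Sixteen scenarios were simulated: baseline normal, truncated to 4–10, mean 6.5 or 7.5, SD 1.5 or 2; percent reduction with mean 45% or 60% and SD 25 or 35 points.

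| Percent reduction | R² | Gain from 80% power (points) |
|---|---|---|
| independent of baseline | 5–16% | +2 to +6 |
| falls 4 points per baseline SD | 2–9% | about +1 to +4 |
| falls 8 points per baseline SD | 0.6–4% | +0.2 to +1.6 |

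Check of the ends: R² = 0.16 gives Φ(2.80/√0.84 − 1.96) = 86.4%; R² = 0.006 gives 80.2%.

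Non-responder imputation weakens the link. With 15% of subjects assumed to be counted as non-responders regardless of baseline, R² falls by about a quarter. So 16% becomes 12% (+4.8 points) and 5% becomes 3.75% (+1.5); in the third row, 4% becomes 3% (+1.2).

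These figures credit baseline with its whole R², not the increment over vIGA-AD. In that respect they are generous.

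**4. Direct simulation, 325 per arm.**

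- Logistic standardisation on continuous baseline NRS with a robust standard error (3,000 trials in each of four scenarios, vIGA-AD left out of both analyses): variance of the risk difference fell 7–11% and power rose 2–6 points. Rejection under the null was 4.7–5.4% adjusted and 4.9–5.5% unadjusted.
- CMH by vIGA-AD and baseline quartile (1,500 trials per scenario; mean baseline 6.5 to 7.5, SD 1.3 to 2; mean reduction 50% against 58% or 60%, SD 30 or 40 points; same percent effect at every baseline): variance fell 0.5–8% and power rose 0.6–4.2 points, for example from 72.1% to 75.3%. In 6,000 null trials, upper-tail rejection was 2.2% for the planned CMH and 2.4% with quartiles added, against a nominal 2.5%.

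**5. EASI 75.** This criterion is already relative to baseline. Assuming the same percent effect at every baseline (baseline EASI mean 29, SD 11; mean reduction 75% against 85%, SD 33 points), R² was 0.3% and power was 86.3% without and 85.6% with baseline quartiles: no gain. If percent reduction falls 8 points per baseline SD, EASI 75 has R² of about 4% (84.4% to 85.2%), while itch drops to about 1% (83.7% to 83.5%). With 1,500 trials, one power figure has a standard error of about √(0.86·0.14/1500) = 0.9 points, so differences this small are close to noise.

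**The case against.** The strongest reply is that nothing in the plan is wrong. A CMH test stratified by a randomisation factor is valid, and the primary endpoint has power to spare. Itch is already tested with baseline adjustment at ranks 1, 4 and 6 through the MMRM. The endpoint at issue is ranked last. All of this stands, and it keeps the point small.

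A reader might infer that the omission costs most for the itch endpoint. The documents do not support that as a fact. It holds if percent reduction does not depend on baseline, but the order reverses in the simulation where subjects with worse baseline improve less in percent terms. No figure in either document decides between the two.

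A reader might also infer a sizeable gain for the primary endpoint by assuming a correlation of 0.4 to 0.5 between baseline EASI and response. Those values mean R² of 16% to 25%, and the documents give no correlation at all. Nor does the contrast of 100% with 40% show a faulty test: it describes the endpoint definition, which a covariate does not change.

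Two practical objections also stand. First, SAP 4.0 puts all randomised subjects in the ITT Population, and SAP 8.2.1 counts a missing baseline as non-response; a model with continuous baseline would drop such subjects unless a rule is given. Second, the change would come late. SAP version 2.0 is dated 02 November 2020. If LSFV in Appendix E means last subject first visit (5 May 2020), then 35 days of screening plus 168 days of treatment ends on 24 November 2020. That argues for adding a supportive analysis rather than replacing a confirmatory test.

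**Conclusion.** The point holds as a modest improvement. Every responder endpoint is adjusted for vIGA-AD only, and none for its own baseline score. For the itch responder endpoint this probably leaves usable information aside, worth about 0 to 6 power points from 80%: +2 to +6 if percent reduction is independent of baseline, +0.2 to +1.6 if it falls 8 points per baseline SD, and less once non-responder imputation is applied. For EASI 75 little or no gain is expected.

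The gap in the plan is certain. Its size rests wholly on assumed itch distributions. There is no bias, no type I error inflation and no shortfall against the stated power.

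**What to change.** Before the Week 24 database lock and unblinding, add to SAP 8.4 for the endpoint of NRS improvement of at least 4:

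- A risk difference standardised to the analysis population, from a logistic model with treatment, vIGA-AD and continuous baseline weekly NRS, with a robust standard error, combined over the imputed datasets by the Rubin step in Appendix F 2.5.2.
- Its status: at least a supportive analysis reported beside the vIGA-AD-stratified CMH.
- A rule for missing baseline, for example non-responder with a missing-baseline indicator in the model. This is not needed if the endpoint is restricted to baseline NRS of at least 4. Protocol 3.3 and SAP Appendix I 1.4 state that restriction; SAP 3.2 and 8.4.1 omit it. The denominator should be made consistent in any case, since a subject below 4 cannot drop by 4.

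A simpler alternative is to add baseline NRS categories as CMH strata, which usually recovers less. The same model with baseline EASI for the EASI responder endpoints is optional.

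The cost is a paragraph of SAP text and modest programming, with no new data. The one drawback is that a standardised risk difference is less familiar than CMH.
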